### **7.4.2.3 Evaluations for Subjects Randomized to Arm 1 Who Do Not Start Study Treatment**

Subjects with recent HIV infection randomized to Arm 1 (immediate treatment) who do not start study treatment will be followed according to the originally specified schedule of evaluations.

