### **11.3 SAMPLE SIZE AND ACCRUAL**

Our goal is to enroll approximately 75-90 men with AHI and 75-90 with RHI in three years, with a target of enrolling 25-50 men with AHI and 25-50 men with RHI per year, or approximately 2-4 men in each group per month. We expect that another 50 men will be identified with acute or recent HIV-1 infection who will either not meet all inclusion requirements or who will not consent to enrollment in the study. Specimens for sequencing will be collected from all men.

Samples for sequencing will be obtained from all identified HIV+ partners of the 200 men with acute/recent infection (we anticipate that not all men will consent to partner tracing). Our initial sequencing efforts will focus on the 100 acutely infected men (75 enrolled plus 25 non-enrolled in immediate/deferred ART study) and their HIV+ partners (especially those with acute or recent HIV infection), testing a total of 400 samples. The first available sample will be sequenced with 454/pyrosequencing and analyzed as described below.

Semen HIV VL will be measured in samples from 60 (30 acute/30 recent) men in the immediate ART group and 60 (30 acute/30 recent) men in the deferred treatment group using established procedures in The University of Washington Virology Laboratory [177, 178]. We will seek separate funding to analyze additional samples, including rectal secretions.

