#### **11.5.3 The Impact of Immediate and Early (6 Months after Diagnosis) Antiretroviral Therapy on the Decay Dynamics of HIV Viral Load**

For men with acute/recent infection plasma VL will be measured at 0, 1, 2, 4, 6, 8, 12, 16, 24, 36 and 48 weeks. Semen specimens and rectal secretions will be collected from all men with acute/recent infection at 0, 1, 2, 4, 6, 8, 12, 16, 24, 36 and 48 weeks and stored. Semen HIV VL will be measured in these samples from 60 (30 acute/30 recent) ART-treated men and 60 (30 acute/30 recent) untreated men using established procedures in the University of Washington Virology Laboratory [177, 178]. This sample size is adequate to detect a 1.0-1.5  $\log_{10}$  change in VL associated with ART based on the following: semen viral load peaks about 30 days after infection, with mean 4.5 and standard deviation 1.6 ( $\log_{10}$  copies/ml) [185]. We compute the power of a two-sample t-test comparing two arms (ART vs. no ART) to detect significant difference with type I error 5%. With 30/group we have 66% power to detect a 1.0  $\log_{10}$  change and 94% power to detect a 1.5  $\log_{10}$  change based on a single viral load measure at peak per subject. The power would be greater if we use any summary measure of individual's multiple viral loads, e.g., mean across different time points.) We will seek separate funding to analyze additional samples, including rectal secretions. VL in semen and rectal secretions will be more informative for modeling the potential impact of ART on infectivity during this period than plasma VL as these 3 measures are only modestly related [177, 178].

The viral load trajectory will be plotted for each subject and for plasma, semen and rectal secretions separately. The mean trajectory and its confidence interval will be computed stratified by randomized arm and by acute or recent infection. The first-order rate of decay, the area under the curve, the peak viral load, and the lowest viral load will be computed for each subject and compared across arms. Multiple testing adjustment will be applied to control type I error.

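### Section 11.5.3 labels the semen groups treated and untreated where Section 11.3 uses the assigned groups, and compares AUC and lowest viral load to week 48 although the deferred arm is on ART after week 24

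*Combined protocol and SAP*

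**What the plan says.** **Who is assayed.** Section 11.3 measures semen viral load in 60 "men in the immediate ART group and 60 (30 acute/30 recent) men in the deferred treatment group". Section 11.5.3 describes what is plainly the same assay set as "60 (30 acute/30 recent) ART-treated men and 60 (30 acute/30 recent) untreated men", with the second group worded in full as "30 acute/30 recent) untreated men using established procedures". The counts, the stage split and the laboratory are identical; only the labels differ.

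**How the contrast is described.** Section 11.5.3 bases power on a "two-sample t-test comparing two arms (ART vs. no ART) to detect significant difference with type I error 5"% and then stratifies mean trajectories by randomised arm. Per-subject decay rate, AUC, peak and lowest viral load are compared across arms. No time window is given for any of these. Samples are listed at weeks 0, 1, 2, 4, 6, 8, 12, 16, 24, 36 and 48.

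**Departures from assignment.** Under Section 7.4.2.3, men with recent infection randomised to Arm 1 "who do not start study treatment will be followed according to the originally specified schedule of evaluations". Section 7.4.2.4 likewise invites Arm 2 men who start ART without meeting the criteria to stay in follow-up, and Section 4.2 offers ART early to Arm 2 men who meet its criteria. Section 4.5 says that men who do not reach 48 weeks in their arm are analysed as Section 11 details. Section 11 contains no such rule.

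**Treatment by period.** Sections 6.3.1.1 and 6.3.1.3 give Arm 2 no ART up to week 24 and ART thereafter to week 48. After Amendment Letter #1, acute cases are offered immediate ART and only recent cases are randomised (Sections 4.1 and 6.3.1.1).

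**The concern.** Semen viral load is part of the first primary endpoint (Section 11.2.1), which is framed as immediate versus deferred groups. Two things put that comparison at risk.

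First, the sentence that decides whose semen is assayed uses treatment status. Taken literally, it would let Arm 2 early starters and Arm 1 non-starters be moved or left out. Early starters under Section 4.2 are men whose CD4 count fell or whose disease progressed, so losing them is unlikely to be random. The trial is open-label, plasma results for some visits are returned during follow-up (Section 7.4.3.8), and semen is tested at the end of the study (Section 7.4.3.10). The assayed men could therefore be picked after treatment and plasma response are known, unless a rule fixed in advance prevents it.

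Second, the untreated label fits Arm 2 only to week 24. A measure computed over all 48 weeks mixes a treated-versus-untreated half with a treated-versus-treated half. It no longer estimates the contrast that was powered.

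**Working it through.** **1. The plan's own power figure.** Inputs from Section 11.5.3: semen viral load "with mean 4.5 and standard deviation 1.6" log10 copies/ml, 30 per group, 5% type I error.

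- Standard error of the difference = 1.6 × √(2/30) = 0.413.
- Noncentrality for 1.0 log10 = 1.0/0.413 = 2.42; for 1.5 log10 = 3.63.
- Two-sided t-test on 58 degrees of freedom: power 66.3% and 94.6%.

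The plan states "With 30/group we have 66% power to detect a 1.0" log10 change, and 94% for 1.5. Both figures reproduce, and neither depends on which label is used. The calculation is for one measurement per man at peak, in an ART versus no-ART contrast.

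**2. AUC over 48 weeks.** Suppose the arms differ by a constant D on the log10 scale while Arm 2 is untreated, and by zero once Arm 2 is suppressed. D and its constancy are assumptions; the week boundaries come from the plan.

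- Arm 2 catches up at once: average difference over 48 weeks = 24D/48 = 0.50D.
- The difference falls linearly from D at the week-24 sample to zero at the week-36 sample: (24D + 12 × D/2)/48 = 30D/48 = 0.625D.
- Weeks 0-24 only: 24D/24 = D.

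To show what this does on the plan's scale, hold the SD at 1.6 and 30 per group:

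| D (log10) | Weeks 0-24 | 48 weeks, 0.625D | 48 weeks, 0.50D |
|---|---|---|---|
| 1.0 | 66.3% | 31.9% | 22.2% |
| 1.5 | 94.6% | 60.7% | 43.1% |

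This isolates the shrinkage of the difference. A time average would have its own SD, which the documents do not give, so these are not forecasts of the trial's power.

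**3. Lowest viral load.** Two of the eleven listed samples, weeks 36 and 48, fall when Arm 2 is on ART. Week 48 is about 24 weeks after the planned start. Section 3.3.3 cites about 90% of patients below 50 copies/ml within four months of starting ART, roughly 17 weeks. If that figure carried over, most men in both arms would reach their minimum at or near the detection limit by week 48, leaving little between-arm difference to detect. The figure is not specific to semen or to early infection, so the direction is clear but the size for semen is not.

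**4. Size of the unstated selection.** Semen is assayed in 120 men. Against the 150-180 planned in Section 11.3 that is 120/180 = 67% to 120/150 = 80%. Against the 200-250 expected in Section 4.1 it is 120/250 = 48% to 120/200 = 60%. Between 20% and 52% of men are therefore left out by a rule that is not written down.

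**5. Acute cells.** Section 4.1 says roughly half of the participants had been enrolled. Assume that this point coincides with Amendment Letter #1 and that the arms were split evenly. The deferred acute cell then holds 75/4 to 90/4, about 19 to 23 men, on the Section 11.3 targets. On the Section 4.1 targets it holds 100/4 to 125/4, about 25 to 31. The target is 30. The actual number is not in the documents.

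**The case against.** The strongest reply is that the treated and untreated labels are shorthand for the arms. The same section speaks of two arms, stratifies trajectories by randomised arm and compares summaries across arms. The primary endpoint is stated as immediate versus deferred, and the counts match Section 11.3 exactly. The literal reading also fits badly with sampling to week 48, since a man who completes Arm 2 as planned is not untreated by then. Sections 7.4.2.3 and 7.4.2.4 keep men who depart from assignment in follow-up, which is what an as-assigned analysis needs.

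Most of that stands. A reader might infer that the plan has chosen to group men by treatment received and so breaks the randomised comparison. The documents do not support that: nothing says crossovers are reclassified or dropped, and silence on how the 120 are drawn is not evidence of a non-random choice. Nor do they support a numerical bias from dropping early starters. The early-start rate and the viral-load excess would both have to be assumed, the Section 4.2 criteria are not viral-load thresholds, and leaving out Arm 1 non-starters could pull the other way.

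The reply does not reach the timing problem. If the groups are the arms, week 36 and 48 samples from Arm 2 are on-ART samples by design, and the unwindowed AUC and lowest value include them.

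It is also fair that the first primary objective covers decay under deferred ART, so the late samples have a purpose. That calls for reporting them separately, not for pooling them into the between-arm contrast.

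**Conclusion.** The concern holds in two parts of unequal weight.

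- **Labels and selection.** The mismatch between Sections 11.3 and 11.5.3 is an ambiguity. Selection by treatment received is permitted by the wording but not shown to be intended. The missing analysis-set rule and the missing draw rule for the 120 men are real gaps. No bias figure can be attached to them from the documents.
- **Time window.** This is substantive under either label. Over 48 weeks the AUC difference shrinks to about 50-62.5% of its weeks 0-24 value, assuming a constant early difference that disappears between weeks 24 and 36. The lowest-value comparison is likely to lose most of its contrast in plasma, and by an unknown amount in semen.

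The stated power figures are correct for the single-peak comparison they describe. They do not carry over to 48-week AUC or lowest viral load. The change should be made before semen results are analysed.

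**What to change.** In Section 11.5.3:

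1. Define the semen groups by randomised arm, as in Section 11.3. State in Section 11 that men who depart from assignment are analysed in their assigned arm, so that the reference in Section 4.5 has something to point to.
2. Draw the assayed men within each randomised arm and stage from a fixed random list, set before any semen result is known.
3. Use weeks 0-24 for the between-arm comparison of AUC, peak and lowest viral load. Report weeks 24-48 separately as decay after deferred ART, and treatment-received results as a sensitivity analysis.
4. Limit the randomised acute comparison to men randomised before Amendment Letter #1, state the number available if it is below 30 per cell, and report later acute men separately.

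**Cost.** Wording and a draw list, with no added assays. Weeks 36 and 48 leave the main between-arm contrast, and decay after deferred ART rests on few points (weeks 24, 36 and 48 in the Section 11.5.3 list). The acute cells may be smaller than 30, with power below the stated figures for that stratum.

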in any health clinic or laboratory authorized by the Ministry of Health, and that have had a documented negative result in the past three months, will be enrolled in a 48-week randomized, open-label clinical trial of the effects on the decay dynamics of HIV viral load in plasma, semen and rectal secretions of immediate –ARM 1- vs. deferred (by 24 weeks) –ARM 2- ART, unless ART initiation criteria are met earlier. We expect that approximately 200-250 MSM and transgender women (roughly 100-125 with acute and 100-125 with recent HIV-1 infection) will participate in the study. Those participants, who have started their participation in the study before the approval of **Amendment Letter #1** in this study protocol, will continue their participation as originally programmed. Once the **Amendment Letter #1** is approved for this study protocol, the participants who are eligible for Step 3 will be given treatment the following way: 1) those people diagnosed with **acute HIV infection** will be offered immediate ART (just at time of the enrollment visit or during the next 48 to 72 hours) for the duration of 48 weeks. 2) The people who are diagnosed with **recent HIV infection** randomized to start immediate ART or defer ART initiation until 24 weeks after HIV diagnosis, all of them followed for 48 weeks after which they will continue ART from other sources. Roughly half of these participants have been enrolled to date. These participants will receive Atripla as study drug; participants enrolled after approval of this protocol version will receive Stribild.

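### The semen viral-load power (66%/94% at 30 per group) is right for one unadjusted test of peak, but allows for neither the planned multiplicity adjustment nor the end of randomisation for acute men

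*Combined protocol and SAP*

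**What the plan says.** Section 11.5.3 sizes the semen sub-study at 60 treated and 60 untreated men, each 30 acute and 30 recent. It asserts "This sample size is adequate to detect a 1.0-1.5" log10 change, taking a semen peak with mean 4.5 and SD 1.6 log10 copies/ml. The basis is: "We compute the power of a two-sample t-test comparing two arms (ART vs. no ART) to detect significant difference with type I error 5" per cent. The result, for one peak value per man at 30 per group, is 66% power at 1.0 log10 and 94% at 1.5 log10. The section adds: "The power would be greater if we use any summary measure of individual's multiple viral loads, e.g., mean across different time points".

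The analysis paragraph that follows is wider. "The first-order rate of decay, the area under the curve, the peak viral load, and the lowest viral load will be computed" for each man and compared across arms, and "Multiple testing adjustment will be applied to control type I error". No method, test family or primary summary is named. On infection stage it says only: "The mean trajectory and its confidence interval will be computed stratified by randomized arm and by acute or recent infection".

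Section 11.3 counts "60 (30 acute/30 recent) men in the deferred treatment group". Section 4.1 says that, once Amendment Letter #1 is approved, people with acute infection "will be offered immediate ART (just at time of the enrollment visit or during the next 48 to 72 hours"). Sections 2 and 6.3.1.1 say the same, and all three reserve randomisation after that point for recent infection.

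**The concern.** This power statement is the only justification for the size of the semen sample, and viral load in semen is part of the first primary endpoint (Section 11.2.1). It describes one test at the full 5%, whereas the planned analysis is four comparisons that share a controlled error rate.

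Two further things are open. Power is quoted per 30 although 60 per group are to be assayed, and the plan does not say whether the arm comparison pools acute and recent men. And the 60 v 60 includes 30 acute untreated men, whom the current design no longer produces by randomisation.

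If these points stay open, the primary test could be chosen after the data are seen. Acute men treated without randomisation could also enter a comparison that is read as randomised.

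**Working it through.** **Inputs.** From Section 11.5.3: SD 1.6; differences of 1.0 and 1.5 log10; 30 per group (60 if strata are pooled); alpha 5%; four summaries; three compartments (plasma, semen, rectal secretions). Assumed here: two-sided testing, the adjustment method, the family size, and that SD 1.6 also holds for recent men and for pooled strata. The plan quotes that SD only for the peak about 30 days after infection.

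**Formula.** Two-sample t-test with n per group: df = 2n − 2, noncentrality = difference / (SD × √(2/n)), power from the noncentral t distribution.

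**The plan's own figure.** With n = 30, df = 58 and the critical t is 2.002.
- 1.0 log10: noncentrality 1.0 / (1.6 × √(2/30)) = 2.42, power 66.3% (plan: 66%).
- 1.5 log10: noncentrality 3.63, power 94.6% (plan: 94%).

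Both reproduce. One-sided 5% would give 77.3% and 97.4%, so the plan used a two-sided test.

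**Per-test power for peak under possible adjustments.**

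| Alpha for peak | 30/group, 1.0 | 30/group, 1.5 | 60/group, 1.0 | 60/group, 1.5 |
|---|---|---|---|---|
| 0.05 (single primary, or tested first) | 66% | 95% | 92% | 99.9% |
| 0.05/4 = 0.0125 (four semen summaries) | 44% | 85% | 81% | 99.5% |
| 0.05/12 = 0.0042 (four summaries × three compartments) | 30% | 74% | 69% | 98.5% |

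Holm over four, simulated at 30 per group and 1.0 log10, depends on the other three summaries. Power for peak is 44–45% if they show no effect, 52–53% if they show the same standardised effect, and about 66% if their effect is equivalent to 2.0 log10.

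**Sample size.** For 80% power at 1.0 log10 (80% is a convention, not the plan's target), peak needs 42 per arm at 5% and 59 per arm at 1.25%.

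**Other summaries.** The plan gives no SD for decay rate, AUC or lowest value. Its example, a mean over visits, can be illustrated. Take the eight visits listed from week 1 to week 24, SD 1.6 at each, the same 1.0 log10 difference throughout and an assumed between-visit correlation r. Then SD = 1.6 × √(r + (1 − r)/8). For r = 0.3/0.5/0.7 this is 1.00/1.20/1.37, giving power 97%/89%/79% at 30 per group and 5%. The argument carries over to averages, but not automatically to a slope or a minimum.

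**Baseline covariate.** Section 7.4.1 already schedules semen at week 0. With an assumed correlation r between week 0 and outcome, SD becomes 1.6 × √(1 − r²). Power at 1.0 log10 and 5% is then 70%/78%/92% for r = 0.3/0.5/0.7 at 30 per group, and 95%/97.5%/99.7% at 60.

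**Who is randomised.** Sections 11.3 and 11.5.3 require 30 acute men deferred or untreated. Under Sections 2, 4.1 and 6.3.1.1, randomised acute men can come only from enrolment before Amendment Letter #1. Section 4.1 says about half of participants had been enrolled by then-current count, but gives no number by stage and arm and does not tie that half to the date of the letter.

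**The case against.** The strongest reply is that the multiplicity loss is avoidable. If peak is declared the single primary summary, or is tested first in a fixed sequence, its alpha is the 5% already used, and 66%/94% stands at 30 per group. That is correct. A reader might infer that the plan's figure is wrong, or that the sub-study has 44% power. The documents support neither: the figure is correct for its stated conditions, and 44% belongs to one assumed method and family.

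A reader might also infer the reverse, that pooling to 60 per group settles the matter. It does so under four-test Bonferroni (81%) but not if the family spans three compartments (69%).

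On acute men, the documents are not silent. Suppose the half already enrolled preceded the letter and was randomised 1:1 (assumptions). Then the 75–90 acute men in Section 11.3 imply about 19–22 per arm (75/4 to 90/4). Added to 30 recent men, that is 49–52 per arm and 86–88% power at 5%. Semen is also stored from all men, so more than 30 recent men per arm might be assayed. Both routes are plausible, but neither is in the plan.

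Finally, the first objective is to estimate, and the plan openly reports 66%. That limits the seriousness of the point. It does not make 66% support the word adequate at 1.0 log10.

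**Conclusion.** The point holds in limited form. The stated power is correct for one unadjusted two-sided 5% t-test of peak semen viral load at 30 per group. It makes no allowance for the adjustment planned in the same section, and at 30 per group it supports adequacy only towards 1.5 log10.

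For peak at 1.0 log10, per-test power runs from 66% (no loss of alpha) through 44% (Bonferroni over four) to 30% (over twelve) at 30 per group. At 60 per group the figures are 92%, 81% and 69%. These rest on SD 1.6 applying to recent men and pooled strata, and on families and methods that the plan does not fix.

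The planned 30 acute deferred or untreated men conflict with the current allocation of acute men. The n of a randomised pooled comparison is therefore unknown from the documents. This should be corrected before the semen data are analysed.

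**What to change.** - Name one primary semen summary, computed from post-baseline values (a peak that includes week 0 could be a pre-treatment value) and tested at two-sided 5%. Put the other summaries in a secondary family of stated size with a named adjustment.
- Compare men by assigned randomised arm, stratified by infection stage, with week-0 semen viral load as covariate.
- Include acute men only where they were randomised, state how many there are per arm, and reconcile Sections 11.3 and 11.5.3 with Sections 2, 4.1 and 6.3.1.1.
- Restate the power for that test and that n, labelling the SD and any baseline correlation as assumed.
- Limit the claim of adequacy to the effects that the restated power supports. Limit the sentence on greater power to averages such as the mean or AUC, unless SDs for the other summaries are given.

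The cost is SAP wording and a rewritten power paragraph, which may read less favourably than the present one. No extra patients, visits or samples are needed.

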#### **7.4.3.8 Virologic Studies**

1. Plasma HIV-1 RNA

All HIV-1 RNA testing will be performed using the Abbott *m2000 RealTime* System (Abbott Molecular) at the IMPACTA PERU Clinical Trials Unit Central Laboratory, which

is certified by the U.S. NIH/NIAID/DAIDS Virology Quality Assurance (VQA) Program. The baseline value will be the HIV-1 RNA level at the entry evaluation.

The results from the analysis of Plasma HIV-1 RNA for the visits 0, 12, 24, 36, and 48 will be available at the next follow-up visit to guide the medical management decision-making for each participant, according to the HIV management standards.

The plasma samples for RNA HIV-1 determination from visits 1, 2, 4, 6, 8, 16, and 20 will not be processed in real time. Since these determinations are exclusively research purposes, the samples will be processed at a later time.

2. **Phylogenetic Analyses**

HIV-1 sequencing and phylogenetic analysis will be performed at The University of Washington Molecular Genetics Laboratory

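### No baseline covariate is specified for the between-arm viral load comparison, although week-0 viral load is already collected; adjusting for it could raise the stated 66% power, by an amount the documents do not settle

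*Combined protocol and SAP*

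**What the plan says.** Section 11.5.3 plans semen viral load in "60 (30 acute/30 recent) ART-treated men and 60 (30 acute/30 recent) untreated men". Power is for an unadjusted comparison: "We compute the power of a two-sample t-test comparing two arms", ART against no ART, at a 5% significance level. The semen distribution at its peak, about 30 days after infection, is taken "with mean 4.5 and standard deviation 1.6" log10 copies/ml. For the smaller difference, in log10 units, the plan states: "With 30/group we have 66% power to detect a 1.0". For a difference of 1.5 log10 it gives 94%. Both figures rest on one value per man, taken at the peak. The section adds, without a figure, that a summary over several time points would give more power.

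For the analysis, the same section lists the decay rate, the area under the curve (AUC), the peak and the lowest value, each computed per man and compared between arms with a multiplicity adjustment. Mean trajectories are to be shown by arm and by acute or recent infection. No covariate, model or change from baseline is named for the arm comparison.

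The visit schedule in Section 7.4.1 and the text of Section 11.5.3 both include week 0 for plasma, semen and rectal secretions. Section 7.4.3.8 defines a plasma baseline ("The baseline value will be the HIV-1 RNA level at the entry evaluation"), but Section 11 does not use it as a covariate.

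**The concern.** Viral load varies widely between men in early infection: the plan's own SD at peak is 1.6 log10, larger than the 1.0 log10 difference at the lower end of its target range. Where a man's week-0 value predicts his later values, an unadjusted comparison leaves that predictable variation in the error term and passes any chance imbalance at entry into the estimate.

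The 30-per-group calculation is the one that matters most. It corresponds to a single infection stratum, its power at 1.0 log10 is only 66%, and among men enrolled after Amendment Letter #1 only those with recent infection are randomised (Sections 4.1 and 6.3.1.1). Because the samples already exist, the remedy needs no extra visits or specimens. Leaving the model open also leaves the choice of adjustment to be made after the data are seen.

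**Working it through.** **Inputs from Section 11.5.3.** n = 30 per group, SD = 1.6 log10 (semen, at peak), differences of 1.0 and 1.5 log10, alpha 0.05. Sidedness is not stated; two-sided reproduces the plan's figures and one-sided does not (77.3% and 97.4%).

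**The plan's own figures.** The standard error of the difference is 1.6 × √(2/30) = 0.413, with 58 degrees of freedom and a critical t of 2.002.
- 1.0 log10: noncentrality 1.0/0.413 = 2.42, power 66.3% (stated 66%).
- 1.5 log10: noncentrality 1.5/0.413 = 3.63, power 94.6% (stated 94%).

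**ANCOVA on week-0 viral load.** The residual SD is 1.6 × √(1 − ρ²), where ρ is the correlation between the week-0 value and the outcome. One degree of freedom is lost (57 remain), and estimating the slope inflates the variance by 1 + 1/(2n − 4) = 1 + 1/56. The documents give no ρ, so the whole range is an assumption. For a 1.0 log10 difference:

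| ρ (assumed) | Residual SD | Power |
|---|---|---|
| unadjusted | 1.600 | 66.3% |
| 0 | 1.600 | 65.5% |
| 0.1 | 1.592 | 65.9% |
| 0.3 | 1.526 | 69.6% |
| 0.5 | 1.386 | 77.7% |
| 0.7 | 1.143 | 91.0% |

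Simulation (40,000 runs per value) agrees to within half a point. Break-even with the unadjusted test is at ρ of about 0.13, and 80% power needs ρ of about 0.54. The largest loss is 66.3 − 65.5 = 0.8 points. At ρ = 0.5 the error variance falls by a factor of 0.75, roughly equivalent to 30/0.75 = 40 men per group.

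**Unequal correlation between arms.** If ρ is 0.5 in untreated men and 0 in treated men, with equal SDs, the common slope corresponds to ρ = 0.25 and the mean residual variance factor is (0.8125 + 1.0625)/2 = 0.9375 = 1 − 0.25². Power is then 68.3%, a gain of 2 points.

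**Change from baseline is not a substitute.** With equal SDs at both times, its SD is 1.6 × √(2(1 − ρ)). Power is 52.1% at ρ = 0.3 and 66.3% at ρ = 0.5, so it only matches the unadjusted test at 0.5.

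**Pooled strata (60 per group, same SD).** Power is 92.4% unadjusted. ANCOVA on the week-0 value gives 92.2%, 94.3% and 97.4% at ρ of 0, 0.3 and 0.5.

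**Chance imbalance.** The week-0 SD is not given. If it were also 1.6, the standard error of the week-0 difference at 30 per group would be 0.413, and an imbalance of 0.4 log10 or more would occur in about one trial in three.

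**The case against.** Several objections have force.

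- **A reader might infer that the plan ignores week 0.** It does not. Week 0 is the first point of each trajectory, so it can enter the decay rate and the AUC and may itself be the peak. What is missing is its use as a covariate.
- **A reader might infer that an unadjusted analysis is planned.** The t-test is named only for the power calculation. For the analysis itself, the method is unspecified. An unadjusted power figure is a legitimate planning basis, and an unadjusted comparison of randomised men is valid.
- **A reader might infer that adjustment is sure to raise power.** That depends on a correlation the documents do not give, and there is reason to expect it to be weak for some outcomes. At week 0, acute men may still be rising towards their peak and recent men may be past it. Treated men start within 72 hours (Section 7.4.2.1), and Section 3.3.3 expects about 90% of treated patients below 50 copies/ml in plasma within 4 months. Many lowest values may therefore lie near the assay limit, where week 0 predicts little.
- **The 1.6 is not the spread of entry values.** It is the SD of semen viral load at peak.
- **A stratum covariate cannot improve the 66%.** That figure is for one stratum, where infection stage is constant. The covariate matters only on pooling, where unadjusted power is already 92.4%.
- **Data availability is uneven.** Semen is assayed only in the subset, and rectal assays await separate funding (Sections 11.3 and 11.5.3).

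These points limit the claim about size. They do not remove the case for adjustment, since the worst outcome is a loss of under 1 point. Nor does the pooled 92.4% settle the matter: after Amendment Letter #1 all acute men are offered immediate ART, so a pooled comparison is not fully randomised.

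**Conclusion.** The point holds as an inexpensive improvement to the primary viral load comparison, not as an error that invalidates it. Section 11.5.3 specifies neither a model nor a covariate, and a useful covariate is already being collected. At 30 per group and 1.0 log10, ANCOVA gives between 65.5% (ρ = 0) and 91.0% (ρ = 0.7), against 66.3% unadjusted. These figures assume the plan's SD at peak, equal SDs and correlations in both arms, a linear baseline relation and a two-sided 5% test. With a correlation in the untreated arm only, the gain is much smaller. For peak and lowest viral load it may be negligible.

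Adjustment does not address the lack of randomisation among acute men enrolled after Amendment Letter #1. For them, including week-0 viral load as a covariate does not turn the comparison into a randomised one.

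**What to change.** In Section 11.5.3:

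1. State that arms are compared by ANCOVA, or a baseline-adjusted mixed model, on log10 viral load, with week-0 log10 viral load in the same compartment as covariate. Add acute/recent infection as a covariate when the strata are pooled. Do not use simple change from baseline in its place.
2. Compute the AUC, peak and lowest value from measurements after week 0 only, so that the entry value is not both outcome and covariate. State which visits the decay rate uses.
3. Apply this to plasma and to the 60 + 60 semen subset, and to rectal secretions only if those assays are funded.
4. Show power over a range of assumed correlations that includes zero, and say that the stated 66% is for one stratum of 30 per group.
5. Say that the adjusted comparison is randomised for recent infection, and not for acute men enrolled after Amendment Letter #1.

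The cost is a short paragraph of text and one or two degrees of freedom, at most about 1 point of power. Plasma and semen need no extra samples or assays.
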